### *Patient Disposition*

The flow of patients through the study will be demonstrated using a flow diagram, consistent with the Consolidated Standards of Reporting Trials (CONSORT) statement. This diagram will display number of patients assessed for eligibility, the number of patients who enrolled and randomized in the study and the number of patients who were excluded or otherwise not enrolled. For enrolled patients, the study group allocation will be displayed, along with the number of patients who complete follow-up assessments at each time point. The number of patients in each group who were lost to follow-up or otherwise excluded from analysis will be displayed.

### *Baseline Characteristics*

Baseline characteristics including demographic information, smoking status, cancer type, comorbidities, and baseline PROs score will be summarized by intervention group using descriptive statistics and visual displays. Descriptive statistics for continuous variables will include the number of subjects, mean, standard deviation, median, first and third quartiles, and minimum and maximum values for the observed value. Frequencies and percentages will be calculated for categorical variables.

### *Adjustment of the Intervention Effect*

The primary analyses for all outcomes will be adjusted for the randomization stratification variables: study site (MGH vs Duke vs Penn) and cancer diagnosis (NSCLC vs SCLC and mesothelioma). Small strata will be combined as needed to ensure numeric stability of model estimates. If needed, sensitivity analyses will additionally adjust for baseline characteristics that are imbalanced between treatment groups. Imbalanced characteristics will be identified *a priori* by examining the distributions of baseline characteristics known to be associated with the primary and secondary outcomes by intervention group. Characteristics that are imbalanced to an extent that is considered clinically meaningful will be included as adjustment covariates in addition to study site and cancer diagnosis.

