Stepped Care as a Strategy to Deliver Accessible and Patient-Centered PC

Stepped care is an appealing approach for PC delivery as it would enable all patients with advanced cancer to have some exposure to PC clinicians, thus representing guideline-concordant care. Importantly, stepped care is patient-centered in tailoring the delivery of PC services to patients’ clinical needs. Such a patient-centered approach to integrating palliative and oncology care is quite timely as cancer therapies are becoming more personalized and effective with fewer side effects. For example, patients treated with targeted oral chemotherapies often remain on treatment for years and may see their oncologist only every few months.^{30,31} While these patients may have challenges with the physical and psychological burdens of their cancer, many are unlikely to require monthly visits with a specialized PC clinician.^{32,33} Thus, in the modern era of cancer therapeutics, a stepped care model, in which low intensity PC is delivered to all patients at clinically relevant points when they are likely to have symptoms or concerns about their cancer while reserving a higher level of PC involvement when patients’ health worsens, may be more accessible, efficient, and patient-centered.

Lung Cancer is an Ideal Population in which to Study Patient-Centered PC

The strongest evidence base supporting early integrated PC is among patients with advanced lung cancer, with two randomized trials demonstrating significant improvements in QOL, mood, and EOL care.^{6,34} However, treatment paradigms for patients with advanced lung cancer are changing rapidly.³⁵ Approximately one-third of patients with metastatic lung cancer have gene mutations or fusions that predict responses to targeted oral therapies or express PDL1 and have tumor shrinkage with immune checkpoint inhibitors, both of which can portend a prognosis of several years.³⁶⁻⁴¹ Despite these advances, the majority of patients with advanced lung cancer do not respond to

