novel therapies and have a median survival of approximately one year.⁴² Moreover, these patients often experience a high symptom burden and poor QOL at diagnosis, which intensifies throughout their illness course.⁴³ With the myriad of medical and psychosocial concerns that patients with advanced lung cancer experience, a one-size-fits-all approach to PC is unlikely to be optimal for this population. Rather, a PC delivery model personalized to each patient's disease course and care needs represents a more patient-centered approach for those with advanced lung cancer.

Scientific Premise of the Project

Early integrated PC has been shown to be an effective care model but is resource intensive, which has limited its dissemination in the outpatient oncology setting. Similarly, an insufficient number of trained clinicians has been a longstanding challenge in psychiatry, which led to the development of stepped care models to tailor treatment to the individual patient, ensure access to care, and increase efficiency. Although stepped care has not been specifically tested as a model for delivering PC, it has been used successfully in addressing the psychosocial needs of patients with cancer.^{25-27,44} In addition to increasing access to PC, a stepped care model is a more patient-centered approach by personalizing care to the patients' illness trajectory and needs. Importantly, a limitation of prior research regarding stepped care models is the inclusion of usual care as the control arm in clinical trials. To ensure a stepped care intervention is *as effective* as more resource intensive standard of care interventions requires a non-inferiority study design.¹⁹ Thus, we propose to perform a multi-site randomized trial of stepped PC versus early integrated PC in patients with advanced lung cancer. By demonstrating the non-inferiority of a stepped PC model to early integrated PC, we seek to define a role for this more accessible, scalable and patient-centered approach to PC.

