3.0. Research Subject Selection

We will recruit 510 patients with advanced lung cancer receiving their care at Massachusetts General Hospital, Duke Cancer Center, or University of Pennsylvania Abramson Cancer Center to participate in a multi-center, non-inferiority randomized trial of stepped PC versus early integrated PC. Patients will be randomized in 1:1 fashion and stratified by site (MGH vs. Duke vs. Penn) and underlying diagnosis (NSCLC vs. small cell lung cancer and mesothelioma). As patients with NSCLC have a significantly better prognosis than those with small cell lung cancer or mesothelioma, we will stratify by the underlying diagnosis to ensure adequate and balanced representation between the two study groups.

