5.4. Data Collection

Table 1 depicts the assessments, measurements, and time points for the data collection. We will administer patient-reported measures for 48 weeks from enrollment. We selected a longer administration period in the current study as the median survival for patients with lung cancer is now approximately one year. The study assessment battery takes approximately 20 minutes to complete.

Table 1. Summary of data collection instruments and time-points.

Self-Report Measure	Baseline	Every 6 weeks*	Week 12	Week 24	Week 36	Week 48
Demographic Questionnaire	X					
Self-Administered Comorbidity Questionnaire (SCQ)	X					
Functional Assessment of Cancer Therapy-Lung (FACT-L)*	X	X*	X	X	X	X
Patient Health Questionnaire-9 (PHQ-9)	X		X	X	X	X
Prognosis and Treatment Perceptions Questionnaire (PTPQ)	X		X	X	X	X
Brief Cope	X		X	X	X	X
EuroQol – 5 Dimension (EQ-5D)	X		X	X	X	X
Support Service Utilization Item					X	

*Step 1 patients will complete the FACT-L every 6 weeks for a minimum of 12 months and up to 18 months from enrollment

5.4.1. Data from Electronic Health Record:

Clinical information regarding tumor type (NSCLC, small cell lung cancer, and mesothelioma), current treatment regimen, date of diagnosis of incurable disease,

previous diagnosis of early stage disease, tumor genotype, and ECOG Performance Status will be collected at baseline.

Health care utilization data will be collected after death or at 12-months from the date the last patient enrolled on the study. We will collect data on: (1) outpatient and inpatient PC visits; (2) chemotherapy and radiation therapy administration; and (3) emergency department, hospital and intensive care unit admissions. EOL care measures will include referrals to and length of stay on hospice and location of death.

5.4.2. PC Cost and Resource Utilization Data:

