### Inclusion Criteria:

1. Diagnosed with advanced NSCLC, small cell lung cancer, or mesothelioma, being treated with non-curative intent, and informed of advanced disease within the prior twelve weeks
2. Eastern Cooperative Oncology Group (ECOG) Performance Status from 0 (asymptomatic) to 2 (symptomatic and in bed <50% of the day)
3. The ability to read and respond to questions in English or Spanish
4. Primary cancer care at one of the three participating sites
5. Age > 18 years

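### Tumor genotype and ECOG status are collected at baseline but no SAP model names them, which costs some precision and some protection if week-24 dropout differs by arm

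*SAP*

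**What the plan says.** **Collected.** Protocol 5.4.1 lists, among the health-record items: "previous diagnosis of early stage disease, tumor genotype, and ECOG Performance Status will be collected at baseline". ECOG also limits entry: "Eastern Cooperative Oncology Group (ECOG) Performance Status from 0 (asymptomatic) to 2".

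**Rationale.** Protocol 1.2 states: "Approximately one-third of patients with metastatic lung cancer have gene mutations or fusions that predict responses to targeted oral therapies or express PDL1", and adds of these two groups, "both of which can portend a prognosis of several years". The majority, it says, do not respond to "novel therapies and have a median survival of approximately one year". The same section expects that many patients on targeted oral drugs will not need monthly palliative care (PC) visits.

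**Stratification.** Protocol 3.0 justifies its diagnosis factor this way: "As patients with NSCLC have a significantly better prognosis than those with small cell lung cancer or mesothelioma". The levels are NSCLC versus small cell lung cancer and mesothelioma, so biomarker groups within NSCLC are not separated.

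**Models.** SAP section 8 (Adjustment of the Intervention Effect) says: "The primary analyses for all outcomes will be adjusted for the randomization stratification variables: study site" and cancer diagnosis. Other baseline characteristics enter only sensitivity analyses, only if thought necessary, and only if their imbalance is judged clinically meaningful; no variable and no threshold is named. SAP section 9 gives the week-24 FACT-L regression group, baseline score and stratification factors. The accompanying mixed model has group, time, their interaction and the stratification factors. Protocol 7.5 instead places factors that prove imbalanced inside the primary regression.

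**Description and missing data.** SAP section 8 says: "Baseline characteristics including demographic information, smoking status, cancer type, comorbidities, and baseline PROs score will be summarized by intervention group". Neither variable is in that list or in the missing-data text, which sets an available-data primary analysis without imputation.

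**The concern.** The primary comparison uses only patients with a week-24 score. The protocol expects 35% missing and the SAP 36%, and Protocol 7.4 attributes this mainly to progressive illness or death. Baseline variables that plausibly predict both survival to week 24 and quality of life at week 24 matter here for two reasons:

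- They can narrow the confidence interval that is compared with -4.5.
- If retention depends on these variables and does so differently in the two arms, conditioning on them removes that part of the distortion.

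The SAP's conditional route serves neither purpose well. It is triggered by baseline distributions by arm, and nothing directs it to the patients who remain at week 24. Two arms balanced at randomization could be unbalanced among completers without triggering it. The covariates would also be chosen by looking at the arms of an unblinded trial, although the SAP describes this choice as made in advance. Finally, the SAP and Protocol 7.5 disagree on whether an imbalanced factor belongs in the primary or a sensitivity model.

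**Working it through.** **Inputs from the documents.** Margin 4.5, SD 17.5, true difference 0, one-sided alpha 0.05, 188 evaluable per group, 255 enrolled per group, 36% missing (SAP section 7); biomarker prevalence about one-third (Protocol 1.2).

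**Assumptions.** The documents give no effect of genotype or ECOG on week-24 FACT-L, no ECOG distribution and no retention by subgroup. Biomarker effects of 3, 5 and 10 points, extra explained variance of 2% to 10%, and the retention patterns below are illustrations.

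**1. The plan's figure.** n = 2 × (1.645 + 0.842)² × 17.5² / 4.5², which rounds up to 188 per group. Power at 188 is 80.2%. The figure reproduces.

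**2. Expected completers.** 255 × (1 - 0.36) = 163 per arm. SE = 17.5 × √(2/163) = 1.94. Power = Φ(4.5/1.938 - 1.645) = 75.1%, if 17.5 is the residual SD of the current model. The gap between 163 and 188 is a separate matter; 163 is used here only as the realistic base.

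**3. Precision gain.** Replace 17.5 by 17.5 × √(1 - R²), where R² is variance explained beyond the current model.

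| Extra R² | SE | Power at 163 per arm |
|---|---|---|
| 0% | 1.94 | 75.1% |
| 2% | 1.92 | 75.8% |
| 5% | 1.89 | 76.9% |
| 10% | 1.84 | 78.9% |

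The 90% CI half-width goes from 3.19 to 3.03 at 10%. Reaching 80% would take an extra R² of about 13%. For scale, a binary factor with prevalence one-third explains b² × (2/9) / 17.5² of the variance: 0.7%, 1.8% and 7.3% for b = 3, 5 and 10.

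**4. Chance imbalance.** The SD of the between-arm difference in prevalence is √(2 × (1/3) × (2/3) / 163) = 5.2 percentage points, and the chance of a difference of 10 points or more is 5.5%. Such a difference moves the estimate by 0.3, 0.5 or 1.0 points for b = 3, 5 or 10. The standard error already covers this. In simulation (4,000 trials per setting, true difference -4.5, covariate omitted) the type I error was 5.1% for both b = 5 and b = 10, with a Monte Carlo SE of √(0.05 × 0.95 / 4000) = 0.34 percentage points.

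**5. Retention that differs by arm and biomarker.** Prevalence among completers is p × r₊ / (p × r₊ + (1 - p) × r₋), with p = 1/3. Overall retention is held at 64% in each arm.

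| Retention, biomarker positive/negative: one arm vs the other | Completer imbalance | Shift for b = 3, 5, 10 |
|---|---|---|
| 80%/56% vs 80%/56% | 0 | 0, 0, 0 |
| 85%/53.5% vs 75%/58.5% | 5.2 points | 0.16, 0.26, 0.52 |
| 90%/51% vs 70%/61% | 10.4 points | 0.31, 0.52, 1.04 |

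The largest shift is 1.04/4.5 = 23% of the margin. Its direction depends on which arm keeps more biomarker-positive patients.

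**The case against.** Adjusting for stratification factors and baseline score is a standard, defensible primary model. Several stronger readings that a reader might infer are not supported:

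- **That biomarker status is the protocol's main prognostic divide.** The factor it selects on prognostic grounds is histology, which is stratified on and is in the model. ECOG appears only as an entry limit and a collected field; no text calls it prognostic.
- **That the SAP shuts both variables out.** Either could enter the conditional sensitivity analysis. Protocol 7.5 allows imbalanced clinical factors in the primary regression and plans disease or treatment factors as moderators. The SAP's baseline list is worded as non-exhaustive.
- **That chance imbalance biases the non-inferiority test.** Step 4 shows that it does not. Systematic bias needs retention to differ by arm and by these variables jointly, and the documents offer no evidence that it will. Contact schedules differ between arms by design, so it is possible, but no more than that.
- **That PDL1 should now be abstracted.** The one-third figure pools gene alterations with PDL1 expression, and PDL1 is not on the collection list, so the calculations only approximate the genotype variable held. The SAP describes enrollment in the past tense, so abstraction would probably be retrospective work at three sites, which this point does not justify.

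The SAP also compares week-24 completers with non-completers, lists multiple imputation and joint modeling, and runs a mixed model that uses week-12 scores. These ease the completer restriction, but none specifies genotype or ECOG. What stands is that the existing route is optional, unquantified and aimed at the wrong moment for a dropout problem.

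**Conclusion.** The point holds as a gap in specification with a modest cost. Type I error is not inflated under randomization. Naming the two variables would be worth about 1 to 4 power points (75.1% to between 75.8% and 78.9% at 163 per arm) for an assumed extra R² of 2% to 10%, provided 17.5 is a residual SD. The documents do not say which it is. If it is a raw SD, baseline FACT-L alone gives 81% to 90% power at 163 per arm for an assumed correlation of 0.4 to 0.6, and the remaining gain is smaller. The protection against joint arm-and-biomarker dropout is worth 0.16 to 1.04 points in the two unequal-retention illustrations and nothing if retention patterns match across arms. ECOG has no separate calculation because the documents give nothing to base one on. The change is still worth making because the data are already collected and the present rule would not address such dropout.

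**What to change.** 1. By SAP addendum, before arm-level outcomes are seen, pre-specify ECOG (0, 1, 2) and genotype group (targetable alteration: yes; no; not tested or not applicable) as fixed covariates in the week-24 FACT-L regression and the sensitivity mixed model. Keep the stratification-factor model as a supporting analysis.
2. If arm-level outcomes have already been seen, leave the primary model alone and make the adjusted model a mandatory, named sensitivity analysis.
3. Include both variables in any multiple-imputation or joint model, and list both in the baseline table by arm.
4. Reconcile the SAP's adjustment section with Protocol 7.5 on where imbalanced factors enter, and replace the unquantified imbalance trigger with a stated rule.

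Cost: wording, about four model degrees of freedom (two per three-level factor), and a not-tested category that will partly overlap with the diagnosis factor. No new data collection is needed.

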### *Significance Level and Multiplicity Adjustment*

Statistical significance testing for non-inferiority of the primary outcome will be one-sided with a type I error rate of 0.05. Testing of secondary outcomes will be one-sided for outcomes being tested for non-inferiority and two-sided for outcomes being tested for superiority. The Benjamini-Hochberg false discovery rate (FDR) control approach will be used to interpret results of significance tests of secondary outcomes with an FDR of 0.15. Analyses of exploratory outcomes will not be adjusted for multiple comparisons, and presented results will emphasize estimates and confidence intervals.

### *Scoring of Patient-Reported Outcomes*

Total and subscale scores for patient-reported outcomes including FACT-L, PHQ-9, and Brief Cope will be calculated for each patient/timepoint using published scoring algorithms. When scoring instructions specifically address how missing item responses should be handled in the score calculation, these instructions will be followed. If no specific guidance for handling missing item responses is provided, subscale scores (if applicable) or total scores (for unidimensional scales) will be calculated via single imputation of the mean of observed subscale values if >50% of the subscale items are non-missing. For scales with total scores derived from the sum or average of two or more subscales, the total score will not be calculated unless all subscale scores can be calculated.

Primary analyses of FACT-L scores will utilize the standard published scoring method. Secondary analyses will use an alternative scoring method for surveys that do not meet the above criteria for calculating the total score—i.e., those that have 50% or fewer non-missing responses on one or more subscales. The alternative scoring method allows calculation of the total score if >50% of all items (across all four subscales) are non-missing.

### *Missing Data*

Primary analyses will include available data without imputation of missing data. The characteristics of patients who complete versus do not the week 24 survey will be compared descriptively. Sensitivity analyses will explore how different assumptions about the missing data mechanisms affect estimated outcomes. These sensitivity analyses may include multiple imputation, terminal decline joint modeling, or partially conditional models, which provide estimates of the mean conditional on being alive and observed at each timepoint.

## **9. Statistical Analysis**

### *Primary Outcome*

The primary outcome is patient-reported quality of life at week 24, as measured by the FACT-L. The difference in week 24 means between intervention groups will be estimated using a linear regression model with group assignment (stepped PC vs early integrated PC) and baseline FACT-L score, as well as randomization stratification factors, as main effects. Using the pre-specified non-inferiority margin of 4.5 points, non-inferiority of stepped PC will be established if the lower limit of the 90% confidence interval (CI) for the estimated difference in means is greater than -4.5. The corresponding p-value for non-inferiority will be calculated using a one-sided test of the estimated difference in means against a null value of -4.5 with a significance level of 0.05. Model-based estimates of the mean with 95% CI in each group, the difference in means between groups and its 90% CI, and the p-value will be reported.

To accompany the approach described above, we will also use a linear mixed effects regression model to estimate the difference in week 24 means between intervention groups. This model will utilize FACT-L scores at baseline, week 12, and week 24, with estimation via maximum likelihood. The model will include fixed effects for group assignment (stepped PC vs early integrated PC), time from baseline (in weeks), time-by-group interaction, and randomization stratification factors, as well as random intercepts for each patient. A contrast will be used to estimate the difference in means at week 24, and this estimate will be evaluated for non-inferiority in the same manner described above. This will be reported as a sensitivity analysis for evaluating non-inferiority for the primary outcome.

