## 7. Sample Size

Sample size calculations were performed to detect a non-inferiority margin of 4.5 points on the FACT-L at week 24, assuming a standard deviation of 17.5 points and a between-group difference of 0 points. 188 patients per group were required to achieve 80% power with a one-sided significance level of 0.05. To account for an anticipated 36% rate of missing data at week 24 due to loss-to-follow-up, withdrawal, or death, enrollment of 255 per group (510 total) was planned.

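### The SAP's week-24 mixed-model sensitivity analysis is not baseline-adjusted, so chance baseline imbalance can separate its non-inferiority verdict from that of the primary ANCOVA

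*SAP*

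**What the plan says.** SAP section 9, Primary Outcome, describes two analyses of week-24 FACT-L. The primary one is a linear regression "with group assignment (stepped PC vs early integrated PC) and baseline FACT-L score, as well as randomization stratification factors, as main effects". It uses available data without imputation (SAP section 8, Missing Data).

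The second is a linear mixed model, labelled a sensitivity analysis: "This model will utilize FACT-L scores at baseline, week 12, and week 24, with estimation via maximum likelihood". Its specification reads "The model will include fixed effects for group assignment (stepped PC vs early integrated PC), time from baseline (in weeks), time-by-group interaction", followed by the stratification factors and a random intercept per patient. Baseline FACT-L is not listed as a covariate, and nothing makes the two arms share a baseline mean. The target is the difference in week-24 means, not in change from baseline, and it is judged against -4.5 in the same way as the primary result.

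Baseline questionnaires are completed before randomization (SAP section 4). The three addendum items do not touch this model.

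**The concern.** Because baseline precedes randomization, any difference between the arms in mean baseline FACT-L is chance. The ANCOVA removes its effect. In the mixed model the group main effect estimates that difference freely, and the week-24 contrast (group coefficient plus 24 times the interaction coefficient) passes part of it on. Two analyses meant to answer the same question thus treat baseline differently.

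This matters because of the model's role. The other missing-data analyses in SAP section 8 are ones the plan says it may do; this is the only one it commits to and specifies. With over a third of week-24 scores expected to be missing, readers will use it to see whether the conclusion holds once patients without a week-24 score contribute. If its verdict differs from the primary one, they cannot tell how much is due to missing data and how much to baseline imbalance.

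**Working it through.** **Inputs.** From SAP section 7: the 4.5-point margin; the SD and true difference ("assuming a standard deviation of 17.5 points and a between-group difference of 0 points"); the week-24 missing rate ("To account for an anticipated 36% rate of missing data at week 24"); and 255 patients per group. (Protocol section 7.4 gives 35% missing.) Assumed: 20% missing at week 12, monotone ignorable dropout, equal variances, and a common correlation ρ between visits, as random intercepts imply. No document states ρ, so a range is shown. Stratification factors are ignored.

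**The plan's own figure.** n per group = 2 × [17.5 × (1.645 + 0.842) / 4.5]² ≈ 187.0, rounded up to 188. This agrees with "188 patients per group were required to achieve 80% power with a one-sided significance level of 0.05".

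**Hand check with complete data.** With linear time, visits at weeks 0, 12 and 24 and random intercepts, the week-24 contrast weights the three arm differences by -1/6, 1/3 and 5/6.

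- Its variance factor is (1 + 4 + 25)/36 + ρ/6 = 5/6 + ρ/6. The ANCOVA factor is 1 - ρ². They are equal at ρ = 1/3.
- One point of baseline imbalance implies an expected profile of (1, ρ, ρ), so the contrast moves by -1/6 + ρ/3 + 5ρ/6 = (7ρ - 1)/6, or 0.42 at ρ = 0.5. The ANCOVA moves by 0.

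**With the planned missing data.** Each arm of 255 has 64% with three visits (163), 16% with two (41) and 20% with baseline only (51).

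- ANCOVA: SE = √[2 × 17.5² × (1 - ρ²) / 163]. At ρ = 0.5 this is √(612.5 × 0.75 / 163) = 1.68.
- Mixed model: generalized least squares variance c′(Σ nₚ Xₚ′ Vₚ⁻¹ Xₚ)⁻¹c, summed over visit patterns p in both arms, with V = 17.5²[(1 - ρ)I + ρJ].

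| ρ | SE, ANCOVA | SE, mixed model as written (linear time) | Shift per point of baseline imbalance, as written | SE, common baseline mean (linear time) |
|---|---|---|---|---|
| 0.3 | 1.85 | 1.75 | 0.16 | 1.73 |
| 0.4 | 1.78 | 1.74 | 0.28 | 1.68 |
| 0.5 | 1.68 | 1.73 | 0.40 | 1.60 |
| 0.6 | 1.55 | 1.71 | 0.52 | 1.49 |
| 0.7 | 1.38 | 1.68 | 0.64 | 1.34 |

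**Break-even with the ANCOVA.** It lies at ρ of about 0.44 with 20% missing at week 12, and between 0.39 and 0.48 with 30% to 10% missing there.

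**Size of a typical imbalance.** The SE of the baseline difference is 17.5 × √(2/255) = 1.55 points. An imbalance of that size moves the contrast as written by 1.55 × 0.28 = 0.43 points at ρ = 0.4 and by 1.55 × 0.64 = 0.99 at ρ = 0.7. These are 10% and 22% of the 4.5-point margin.

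**Is this only the linear-time choice?** No. With categorical time and separate baseline means, the shift per point equals ρ itself, and the model is noisier than the ANCOVA at every positive ρ examined (1.83 against 1.68 at ρ = 0.5). With categorical time and a common baseline mean, the SEs at ρ = 0.4, 0.5, 0.6 and 0.7 are 1.76, 1.66, 1.53 and 1.36, slightly below the ANCOVA throughout.

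**The case against.** Several stronger readings are tempting, and the documents do not support them.

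- A reader might infer that the mixed model is always noisier than the primary analysis. It is not. With time linear in weeks, as the SAP words it, the model gains precision from the straight line and from patients without week-24 data. It beats the ANCOVA below ρ of about 0.45, and at 0.5 the loss is only 3% in SE. The gain at low ρ does depend on the model being right: if correlations decay with time (autoregressive), break-even falls to about 0.33 and the model-based SE is too small (1.70 against 1.79 at ρ = 0.5).
- A reader might infer bias. Over repeated randomizations the expected baseline difference is zero, so the free baseline mean adds variance only. The shift from a given imbalance is already inside the model's SE and is not a second harm.
- A reader might infer that the trial loses power. Its conclusion rests on the ANCOVA, which adjusts for baseline. Against that ANCOVA, the repaired linear-time model lowers the SE by only about 3% to 5%.
- A reader might treat baseline imbalance as the only possible cause of disagreement. The mixed model also adds patients, imposes linear time and assumes a covariance structure. Offering a different view under missing data is its purpose.
- A reader might carry these figures over to the 48-week slope model in SAP section 9, Exploratory Outcomes. It has the same form, but it targets a slope, carries no non-inferiority decision, and is not quantified here.

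SAP section 8 also allows sensitivity analyses, if needed, that adjust for clinically meaningful imbalance. That helps in part, but it names no baseline FACT-L term for this model.

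What stands is that only a sensitivity analysis is affected, and that the loss of precision is conditional on ρ. Neither point removes the mismatch in baseline adjustment.

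**Conclusion.** The point holds in limited form. The mixed-model contrast is not baseline-adjusted while the primary analysis is. The SAP's wording alone shows this. Under the assumptions listed, the contrast moves by 0.28 to 0.64 points per point of chance imbalance for ρ from 0.4 to 0.7, and its SE exceeds the ANCOVA's once ρ passes about 0.45. How much precision is lost cannot be settled from the documents, because ρ is not given.

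The case for changing the model does not depend on ρ. Under random-intercept covariance, the common-baseline model is at least as precise as the model as written at every correlation from 0.2 to 0.8, and never noisier than the ANCOVA. The change is worth making so that agreement or disagreement with the primary verdict can be interpreted. It is no reason to doubt the primary analysis.

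**What to change.** In SAP section 9, Primary Outcome, change the mixed model in one of two ways.

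1. Drop the group main effect and keep the group-by-time terms, so that both arms share one baseline mean. Categorical time is preferable.
2. Remove baseline FACT-L from the responses, enter it as a covariate, and use weeks 12 and 24 as outcomes.

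In either case, state whether time is linear or categorical.

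The cost is one line of specification and code, with no new data. The downsides are small. With linear time, the first option forces the arms to diverge along straight lines from a single point. If the true correlation is autoregressive while random intercepts are fitted, it also still carries about -0.07 to -0.11 points per point of imbalance. The second option drops patients with no follow-up score.

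The SAP's dated addendum is a suitable place for the change. If results are already known, report the revised model beside the one in the signed SAP and label it as added later.
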